At the time of this publication the study protocol was approved by all corresponding regulatory authorities and the local ethic committees in Switzerland (BASEC-ID: 2021-00453), Austria (EK Nr: 2136/2021), France (N° de dossier: 21.04056.000061–22014), Germany (Aktenzeichen:

PASTA (Pediatric Arteriopathy Steroid Aspirin) trial

pediatric stroke

Study Protocol

2022-066-f-A) as well as UK (IRAS ID: 305395) and Australia (RCH HREC Reference Number: 78937). The study is registered at ClinicalTrials.gov (NCT04873583).

Patient population

All patients older than 6 months and younger than 18 years with unilateral FCA-i will be screened on admission. The complete eligibility criteria are provided in table 1.

Inclusion criteria	Exclusion criteria
1. Written informed consent (legal representative)	1. Previous stroke
2. Age 6 months to under 18 years	2. Genetic vasculopathies include ACTA2, neurofibromatosis type 1, trisomy 21
3. Randomization possible within 48 hours of diagnosis and maximum 96 hours after symptom onset	3. Moyamoya or sickle cell disease
4. Symptomatic unilateral cerebral arteriopathy (newly acquired neurological deficits of proven ischemia and unilateral stenosis/vessel irregularity on neuroimaging)	4. Craniocervical arterial dissection
5. Female participants age \geq 13: Negative pregnancy test	5. Primary (small vessel) and secondary angiitis of the CNS
	6. Bilateral arteriopathy
	7. Underlying systemic disorders e.g., rheumatological
	8. On steroid treatment at disease onset
	9. Contraindication to corticosteroid treatment
	10. Inability to follow study-procedures
	11. Participation in another interventional study

Table 1: Eligibility criteria

PASTA (Pediatric Arteriopathy Steroid Aspirin) trial

pediatric stroke

Study Protocol

The diagnosis of unilateral cerebral arteriopathy (inclusion criterion 4) will be made on site by the respective study team. If the diagnosis is not clear, the sponsor will be contacted to review the MRI images together with the neuroradiologists at the sponsor's site. Subsequently, the sponsor and study site will seek a joint agreement as to whether or not the patient fulfills the eligibility criteria.

Randomization and blinding

Allocation will be done in a 1:1 ratio of standard care alone (including aspirin) or standard care plus corticosteroids (See Fig. 3) using web-based randomization with secuTrial.

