Probabilistic minimization will be used, accounting for the following stratification factors: age (6 months through 5 years, 6 years through 11 years, 12 years to under 18 years) and pediatric National Institute of Health Stroke Scale (Ped-NIHSS; < 7, 7 to 12, >12).

Trial participants and local data collectors will not be blinded, as steroid treatment causes obvious clinical signs and symptoms. Imaging outcomes will be centrally assessed by blinded neuroradiologists.

The telephone-interview-based assessments of RRQ (Recurrence and Recovery Questionnaire), mRS (modified Rankin Scale) and VABS (Vineland Adaptive Behavior Scales) will be performed

PASTA (Pediatric Arteriopathy Steroid Aspirin) trial

pediatric stroke

Study Protocol

blinded centrally for all study participants.

Intervention

Participants in both study arms will be treated based on standard care, including antithrombotic treatment with daily oral aspirin (3-5mg/kg/day, maximum 150mg/day). The hyperacute treatment (including intravenous thrombolysis and endovascular thrombectomy) may be performed according to local protocol. Start with any type of anticoagulation is possible and should be done as by local protocol. Switch or start of aspirin is mandatory at latest at inclusion. Suggestions (see supplementary) for standard care are given to the sites but noncompliance is not a deviation to the protocol. These suggestions have been discussed and approved by the international steering committee of the PASTA trial (see Appendix 1).

In addition, participants in the treatment arm will receive 3 days of intravenous methylprednisolone 30mg/kg/day (max. 1000mg/dose) in one daily dose. This is followed by therapy with oral prednisolone 1 mg/kg/day (max. 40mg/day) for 2 weeks and 0.5mg/kg/day (max. 20mg/day) for another 2 weeks.

Outcomes

The Primary Outcome is the change in FCASS from baseline examination to 1 month. In

PASTA (Pediatric Arteriopathy Steroid Aspirin) trial

Pediatr Stroke. 2023;6: 21-42

www.pediatricstrokejournal.com

addition, various imaging data, clinical and safety outcomes will be assessed (see table 2).

Primary Outcome

● Change in FCASS from baseline to 1 month
Secondary Outcomes
Imaging

● Change in FCASS from baseline to 6 months● Volume of stroke (in FLAIR and DWI-sequences) at baseline, 1, 3 and 6 months by modified pediatric ASPECTS● Residual arteriopathy at 6 months by FCASS
Clinical

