Central data monitoring and validation will be performed according to a separate monitoring plan continuously for each site. This will include regular verification of the completeness, accuracy, and plausibility of the entered data and to query the site and follow up anything requiring clarification. No interim analyses are planned and no safety stopping points are defined.

Sample size estimates

For 13 patients of a retrospective study the standard deviation of the change in FCASS from baseline to maximum severity of arteriopathy was 2.8.¹⁴ Based on this standard deviation and a two-sample means test, 64 patients (32 in each group) are required to detect a difference of 2.0 with a power of 80% at a two-sided alpha-level of 0.05.

PASTA (Pediatric Arteriopathy Steroid Aspirin) trial

pediatric stroke

Study Protocol

To account for dropouts (8%), we will enlarge the sample size to 70 patients (35 in each group).

Statistical Analyses

The primary analysis will follow the intention-to-treat (ITT) principle. The primary outcome and secondary continuous variable outcomes that are measured multiple times during follow-up will be assessed in a repeated-measure, mixed-effects linear model.

Neurocognitive outcomes measured at 1 year will be analyzed using a mixed-effects linear model, binary outcomes (recovery, residual arteriopathy) will be assessed using generalized linear mixed-effects models, Time-to-event outcomes (stroke recurrence, infection requiring hospitalization, progressive arteriopathy) will be analyzed using Cox-regression, accounting for the stratification factors used at randomization (country and baseline FCASS).

We will perform a subgroup analysis according to baseline FCASS (<8 vs ≥8), accompanied by an appropriate test of interaction. Moreover, we will test whether the baseline FCASS (used continuously) has an influence on the association between steroid treatment and modified ASPECT score, i.e. whether there is effect modification (interaction).

Scores measured repeatedly over time (FCASS, mRS, PSOM, VABS, modified pediatric ASPECT) might be considered as categories. Patients may shift from category to category several times

PASTA (Pediatric Arteriopathy Steroid Aspirin) trial

pediatric stroke

Study Protocol

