over the duration of follow-up. We will additionally use mixed effects ordered logistic regression analysis on this data (shift analysis). Moreover, we will perform subgroup analysis according to country and baseline FCASS (<8 vs ≥8).

Discussion

Treatment of pediatric stroke is limited to secondary prevention in the vast majority of cases.²⁴⁻²⁶ In contrast, treatment of FCA-i with steroids would be a therapy that directly intervenes in the acute course of the disease. There is much experience with the steroid dosing regimen, which is consistent with standard practice for other immunotherapy treatment protocols in children.^{27,28} But there is no evidence for this treatment in FCA-i. Despite this lack of evidence, a recent review (meta-analysis) on immunotherapy in pediatric stroke has shown that 80% of children with FCA-i were treated with corticosteroids.² For this reason, and because of the fact that FCA-i is at high risk for stroke recurrence, the project that we present here has been identified as the most important pediatric trial for the treatment of AIS.^{4,29} Aside from the trials of stroke prevention in sickle-cell disease³⁰, this is one of the first randomized, controlled treatment trials in pediatric AIS. In addition, the PASTA study is generating one of the largest prospective cohorts of patients with FCA-i. This will make it possible to systematically study FCA-i in an unprecedented way and to obtain a better insight into the pathophysiology of FCA-i.

PASTA (Pediatric Arteriopathy Steroid Aspirin) trial

Pediatr Stroke. 2023;6: 21-42

www.pediatricstrokejournal.com

pediatric stroke

Study Protocol

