Nevertheless, the study has some limitations. The diagnosis of FCA-i remains challenging in the acute setting for the following reasons: According to the traditional definition, the disease is monophasic - this cannot be detected in the acute situation. Imaging findings often overlap with intracranial dissection, so that differentiation is often difficult. Moyamoya is differentiated from FCA-i by the presence of collateral vessels. However, these may be absent in early stage moyamoya.³¹ Biomarkers such as varicella serology in CSF are only effective in certain cases.³² In recent years, vessel wall imaging has been increasingly used as a diagnostic biomarker.³³ However, vascular wall imaging with contrast enhancement cannot be performed within a study setting for ethical reasons. Overall, the diagnosis is therefore still often based on expert opinion by experienced stroke specialists. Accordingly, the inclusion criteria for this study were defined more broadly - so that the presence of unilateral arteriopathy after exclusion of any differential diagnoses is sufficient. As a support the centers will be guided in diagnosis by the sponsor team and their neuroradiologists experienced in this diagnosis.

As FCA-i is a rare disease, the number of cases in each center included in the study is very low. This means that the experience of the investigators of the individual centers in handling the study will be low and stratification by center is not possible. This and the lack of complete blinding of the investigators increases the risk of observer bias. Since the imaging outcomes and

PASTA (Pediatric Arteriopathy Steroid Aspirin) trial

Pediatr Stroke. 2023;6: 21-42

www.pediatricstrokejournal.com

thus the primary outcome are collected centrally, they are not affected by this risk. To reduce risk in recording clinical outcomes, investigators were provided with videos for learning the ped-NIHSS and PSOM in a standardized manner. In addition, the collection of various clinical outcomes is done centrally via telephone interview by a blinded investigator. As a further limitation, it should be mentioned that a surrogate marker was chosen as the primary outcome here. However, it could be shown that this correlates with the clinical outcome and that this has a high reliability.^{12,14} In addition, to validate the results of the primary outcome, various clinical outcomes will also be assessed in the PASTA study.

Summary and conclusion

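### The protocol gives two non-overlapping lists of randomization factors: age and Ped-NIHSS for the allocation, country and baseline FCASS for (at least) the Cox models

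*Protocol*

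**What the plan says.** Protocol, Randomization and blinding: allocation is 1:1 through secuTrial. The rule reads "Probabilistic minimization will be used, accounting for the following stratification factors: age", with age cut into three bands. The second factor is stroke severity in three categories, given as "pediatric National Institute of Health Stroke Scale (Ped-NIHSS; < 7, 7 to 12, >12"). No other factor is named there.

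Protocol, Statistical Analyses: the first model sentence gives the primary outcome and the repeatedly measured continuous secondary outcomes a repeated-measures mixed-effects linear model and names no covariates. The next sentence covers neurocognitive outcomes (mixed linear model), binary outcomes (generalized linear mixed models) and time-to-event outcomes (Cox regression). It ends with "accounting for the stratification factors used at randomization (country and baseline FCASS").

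Elsewhere in that section, country and baseline FCASS appear only as subgroup or effect-modification variables, for example "we will perform subgroup analysis according to country and baseline FCASS (<8 vs ≥8"). The Discussion adds that "stratification by center is not possible" because each center contributes few cases; it does not mention country. No section puts age or Ped-NIHSS into any analysis model.

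**The concern.** Both sections claim to report the same fact, namely which variables the allocation used. They cannot both be right, and an analyst cannot follow both.

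Minimization forces the arms to be similar on its factors. If those factors predict the outcome and the model omits them, the model-based standard error still includes variation between arms that the design has largely removed. It is then too large: tests reject too rarely, intervals are too wide, and some precision is given away. A statistical analysis plan that took its covariates from the Statistical Analyses section would inherit the mismatch. Once outcome data exist, choosing between two published covariate lists could also look data-driven.

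**Working it through.** **1. The two lists side by side**

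| | Randomization and blinding | Statistical Analyses |
|---|---|---|
| Factor 1 | Age, 3 bands | Country, levels not listed in the clause |
| Factor 2 | Ped-NIHSS, <7, 7 to 12, >12 | Baseline FCASS, no cut-point in the clause |
| Presented as | Factors of the minimization | Factors used at randomization |

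Overlap: 0 of 2. The randomization section names the method and gives full cut-points, so the analysis clause is the likelier leftover. The document alone cannot prove that.

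**2. The plan's own figure, as a baseline.** Sample size estimates gives SD 2.8, difference 2.0, two-sided alpha 0.05 and power 80%. A two-sample t-test with standardized difference 2.0/2.8 = 0.714 needs 31.76, so 32 per arm and 64 in total. Power at 32 per arm is 80.3%. Allowing for 8% dropout, 64/0.92 = 69.6, so 70. The plan's figures reproduce, and this point does not change them.

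**3. Direction and rough size of the effect.** Let R² be the share of outcome variance explained by the two minimized factors. With near-perfect balance, the true standard error of the treatment difference is about √(1 − R²) times the one reported by a model that omits them. The true type I error is then about 2Φ(−1.96/√(1 − R²)):
- R² = 0: 5.0%
- R² = 0.2: 1.96/0.894 = 2.19, giving 2.8%
- R² = 0.4: 1.96/0.775 = 2.53, giving 1.1%

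**4. Simulation with imperfect balance.** From the protocol: 64 children, SD 2.8, difference 2.0, two 3-level factors, 6 countries. Assumed: preferred-arm probability 0.8, equal level and country frequencies, a linear outcome, country and baseline FCASS unrelated to outcome, and R² varied because the protocol does not give it. There were 4,000 runs per scenario, so the Monte Carlo standard error near 5% is √(0.05 × 0.95/4000) = 0.34 points.

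| R² | Type I error, country + FCASS | Type I error, age + Ped-NIHSS | Power, country + FCASS | Power, age + Ped-NIHSS |
|---|---|---|---|---|
| 0 | 4.3% | 4.4% | 76% | 80% |
| 0.1 | 3.6% | 4.7% | 76% | 84% |
| 0.2 | 3.1% | 5.1% | 78% | 88% |
| 0.3 | 2.7% | 5.4% | 78% | 92% |
| 0.4 | 1.7% | 5.0% | 80% | 95% |

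**5. Sensitivity to baseline FCASS.** If baseline FCASS instead explains 20% of the variance (3,000 runs, R² from 0 to 0.3), power is 85–89% with country + FCASS and 81–92% with age + Ped-NIHSS alone. The country + FCASS model is ahead at R² of 0 and 0.1, and the two tie at 87% at R² = 0.2. Its type I error is still only about 2–3% at R² of 0.2 to 0.3. The conservatism therefore persists, but the power gap does not.

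**The case against.** The contradiction itself has no defence in the text. The objections concern how far it reaches and how much it costs, and most of them stand.

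- **Reach.** A reader might infer that the primary analysis conditions on the wrong factors. The document does not show this. The clause closes the sentence on secondary outcomes, directly after Cox regression. It governs those models, or at most its own sentence. The primary outcome is in the preceding sentence, where no covariates are named, and a statistical analysis plan not at hand may supply them.
- **Size.** A reader might take a loss of 10 or more points of power from the table. That gap applies a linear model with the primary outcome's figures, although the clause is attached with certainty only to Cox models, for which no type I error or power was computed. It also needs R² of about 0.2 or more and a non-prognostic baseline FCASS, which is hard to assume for the baseline value of the primary outcome. Even then the country + FCASS model has 76–80% power against a planned 80%; most of the gap is a gain above plan.
- **Country.** A reader might conclude that country must be dropped because the Cox models are sparse. With an assumed event risk of 10–15% and six equal countries, the chance of at least one country without events is 1 − (1 − (1 − p)^(70/6))^6, or 87% to 62%. Such a country affects its own coefficient; the treatment hazard ratio remains estimable, and a stratified Cox model has no country coefficients at all. Age, Ped-NIHSS and continuous FCASS together would also spend 2 + 2 + 1 = 5 parameters on the same 7–10 events. Treating the two 3-level factors as independent with equal thirds, the chance of an event-free level is 1 − (1 − (1 − p)^(70/3))^6, or 42% to 13%.

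**Conclusion.** The plan is wrong as written: two sections state different randomization factors, and only one statement can be true. This rests on the text alone and needs no assumption. It is certain for the Cox models (stroke recurrence, infection requiring hospitalization, progressive arteriopathy) and unclear for the other models, including the primary one. That lack of clarity should be removed in the same correction.

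If the randomization section is operative, the expected consequence is conservative inference and some lost precision, not a biased treatment effect or excess false positives. The type I error of about 4.3% down to 1.7% for R² of 0 to 0.4 is illustrative, under the linear-model assumptions set out above. The document does not support a stated loss of power for the primary analysis, nor a finding that adjusting for country is an error. Adjusting for baseline FCASS is not harmful in itself; the error lies in presenting it and country as randomization factors while leaving out the factors named for the minimization.

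**What to change.** 1. Check the minimization as configured in secuTrial. Trial status reports 7 participants already randomized, so the set-up is live and can be read directly.
2. If it matches Randomization and blinding, change the parenthesis in Statistical Analyses from country and baseline FCASS to age group and Ped-NIHSS category. If it uses country and baseline FCASS, correct Randomization and blinding instead.
3. State which models the adjustment covers, and say explicitly whether the primary mixed model is among them.
4. Baseline FCASS may stay as a named prognostic covariate. If the configuration matches Randomization and blinding, neither it nor country should be described as a randomization factor.
5. Decide separately, as a modelling choice, whether country stays in the sparse Cox models.

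The cost is one configuration check and a sentence or two in the protocol, carried into any statistical analysis plan. No extra data are needed and the sample size stays at 64 evaluable and 70 enrolled. The correction is best made before outcome data are examined, so that the covariate set is clearly prespecified.
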